7.5. Pooling of Centers

Data from all sites will be summarized together for analyses.

7.6. Subgroups

No subgroup analyses are planned for this study.

However, a few key summary analyses may be repeated to include subjects who received AP-PA02 and were dosed prior to the first DSMB meeting as a sensitivity analysis.

This document is confidential.

8. Demographic, Other Baseline Characteristics and Medication

8.1. Subject Disposition and Withdrawals

A summary table will be produced detailing the number of subjects screened and screen failed, the number and percentage of all subjects in each analysis population, subjects who completed or discontinued study treatment, subjects who completed or who prematurely discontinued the study. In addition, reasons leading to discontinuation from study and study treatment discontinuation will be summarized for each cohort and overall. A listing of subject disposition will also be provided.

Screened subjects are defined as all subjects with a non-missing informed consent date and screen failures are defined as all subjects who sign the informed consent but are not enrolled into the study.

8.2. Demographic and Baseline Characteristics

Descriptive summaries of demographic and baseline characteristics will be presented by each cohort and overall, for the Safety Population. The demographic data includes: age at screening (in years), sex at birth, race, ethnicity/geographic origin (North East Asian or South East Asian), height (cm), weight (kg), BMI (kg/m²), and for females, childbearing potential. Baseline disease characteristics include forced expiratory volume [FEV₁ (L)], forced expiratory volume (FEV₁) % Predicted, forced vital capacity [FVC (L)], forced expiratory flow between 25 and 75% of the FVC [FEF₂₅₋₇₅ (L)], Quality of Life Bronchiectasis (QOL-B) scale scores, Leicester Cough Questionnaire (LCQ) score, and Saint George's Respiratory Questionnaire (SGRQ) score.

Height (in m) = height (in cm) / 100

BMI (kg/m²) = Weight(kg)/[Height(m)²]

Demographics and Baseline characteristics will be listed by subject for the Safety Population.

8.3. Medical History

Medical History will be summarized for the Safety Population using Medical Dictionary for Regulatory Activities (MedDRA) system organ class (SOC) and preferred term (PT). The reported medical history terms will be coded using MedDRA Version 25.0 or higher. The number of subjects with any medical or surgical history will also be summarized. A subject experiencing a medical history within more than one SOC and PT will be counted only once within that SOC and PT, respectively.

Medical history findings will be listed by subject using the Safety Population.

8.4. Medication

Medications used within 30 days prior to Screening will be recorded.

All prior and concomitant medications will be classified using the anatomical Therapeutic Chemical (ATC) classification codes and preferred drug names from the World Health Organization Drug Dictionary (WHO-DD), March 2022.

Summaries of prior and concomitant medications will be presented separately in tabular form using the ATC 4 level term as an upper classification level and the preferred drug name as a lower classification level. If the medication does not have an ATC level 4 term, the ATC level 3 term is used. If the ATC level 3 term is also unavailable, the ATC level 2 term is used. All medications will be summarized by

This document is confidential.

descending frequency of ATC level 4 and preferred drug name within a given ATC level 4 term. The summary will consist of the frequency and percent of safety subjects who used the medication at least once.

For each subject, the medication will be counted only once within a level 4 ATC and only once within a given preferred drug name level. A subject may appear more than once if he/she has more than one concomitant medication coded under different ATC categories; however, the subject will be counted only once in the overall category.

A by-subject listing with coded terms will also be provided along with calculated study day.

The coronavirus disease 2019 vaccination status (including type of vaccine and administration date[s]) of all subjects will be recorded as a prior (if received prior to dosing) and/or concomitant medication.

8.4.1. Prior Medication

Any medication that started prior and did not continue past the first dose of study treatment will be classified as prior.

8.4.2. Concomitant Medication

Any treatment given in addition to the study drug during the study will be regarded as a concomitant medication and must be recorded on the appropriate electronic case report form (eCRF). All medications taken during the study treatment period, including those which started before study treatment but continued past or started on or after the first dose date of study treatment, will be classified as concomitant.

8.5. Extent of Exposure

Prior to the first DSMB meeting, the AP-PA02 dose was administered to each subject as 2 fractionated doses per treatment day. The dosages shown below are estimated (approximate) plaque-forming units (PFU):

- Each fractionated dose: 1.5×10^{11} PFU;
- Total dose per treatment day: 3×10^{11} PFU; and
- Total dose per 10-day treatment course: 3×10^{12} PFU.

After the first DSMB meeting, the dose was doubled.

AP-PA02 will be administered in the clinic [REDACTED] during Visit 1/Day 1 (both doses), Visit 2/Day 5 (morning dose only), and Visit 3/Day 10 (morning dose only). Subjects will administer AP-PA02 at home on all other treatment days.

The placebo [REDACTED]

This document is confidential.

The placebo will be administered in the clinic/at home using the same fractionated dosing schedule and duration as AP-PA02 [REDACTED]. The placebo will be administered in the clinic during Visit 1/Day 1 (both doses), Visit 2/Day 5 (morning dose only), and Visit 3/Day 10 (morning dose only). Subjects will administer placebo at home on all other treatment days.

Subjects in Cohort A will receive study treatment (AP-PA02 or placebo) administered as 1 dose distributed over 2 administrations given 6 hours apart on the same day on Day 1 and 10-12 hours apart each day on the remaining days on 10 consecutive days, with 28 days of follow-up after the last treatment. Subjects in Cohort B will receive study treatment (AP-PA02 or placebo) administered as 1 dose distributed over 2 administrations given 6 hours apart on the same day on Day 1 and 10-12 hours apart each day on the remaining days for 10 consecutive days plus their current antipseudomonal inhaled antibiotic for 28 days (10 days of treatment plus an additional 18 days).

Treatment exposure will be summarized using the treatment duration (days), total dose administration time (minutes), and number of doses for the Safety Population. Treatment duration is the number of days between first and last treatment inhalation, defined as the last inhalation date – first inhalation date + 1. Dose administration time is the elapsed time between start time and stop time of treatment administration, defined as stop time (HH:MM) – start time (HH:MM), and will include dose interruption or delay, if any occurred. Total dose administration time will be calculated utilizing the time of administration from only the first dose of each day and then summing these times over the total treatment duration. Continuous variables will be summarized with descriptive statistics of mean, SD, median, minimum, and maximum.

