5.5.3 Study Drug Administration

The AP-PA02 dose will be administered to each subject as 2 fractionated doses per treatment day. The dosages shown below are estimated (approximate) PFU:

- Each fractionated dose: 1.5×10^{11} PFU;
- Total dose per treatment day: 3×10^{11} PFU; and
- Total dose per 10-day treatment course: 3×10^{12} PFU.

AP-PA02 will be administered in the clinic [REDACTED] during Visit 1/Day 1 (both doses), Visit 2/Day 5 (morning dose only), and Visit 3/Day 10 (morning dose only). Subjects will administer AP-PA02 at home on all other treatment days.

The placebo will be administered in the clinic/at home using the same fractionated dosing schedule and duration as AP-PA02 and [REDACTED]. The placebo will be administered in the clinic during Visit 1/Day 1 (both doses), Visit 2/Day 5 (morning dose only), and Visit 3/Day 10 (morning dose only). Subjects will administer placebo at home on all other treatment days.

On Visit 1/Day 1, clinic staff will administer the first dose of AP-PA02 or placebo. The subject and/or caregiver will administer the second dose of AP-PA02 or placebo with clinic staff observation after the subject has been trained on proper administration. Clinic staff will confirm

the subject/caregiver is comfortable with administering AP-PA02 or placebo during this visit. If the subject is not comfortable administering AP-PA02 or placebo, the subject may visit the clinic for study drug administration until he/she or the caregiver is comfortable with proper study drug administration.

Subjects in Cohort A will receive study treatment (AP-PA02 or placebo) administered as 1 dose distributed over 2 administrations given 6 hours apart on the same day on Day 1 and 10-12 hours apart each day on the remaining days on 10 consecutive days, with 28 days of follow-up after the last study drug dose. Subjects in Cohort B will receive study treatment (AP-PA02 or placebo) administered as 1 dose distributed over 2 administrations given 6 hours apart on the same day on Day 1 and 10-12 hours apart each day on the remaining days for 10 consecutive days plus their current antipseudomonal inhaled antibiotic for 28 days (10 days of study drug treatment plus an additional 18 days). Subjects in Cohort B will also have 28 days of follow-up after the last study drug dose.

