8.6 Special Situation Reports

Special situation reports include reports of overdose, misuse, abuse, medication error, and reports of adverse reactions associated with product complaints.

- **Overdose:** Refers to the administration of a quantity of a medicinal product given per administration or cumulatively (accidentally or intentionally), which is above the maximum recommended dose according to the Protocol. Clinical judgement should always be applied. In cases of a discrepancy in the drug accountability, overdose will be established only when it is clear that the subject has taken additional dose(s), or the Investigator has reason to suspect that the subject has taken additional dose(s).
- **Misuse:** Refers to situations where the medicinal product is intentionally and inappropriately used in a way that is not in accordance with the Protocol instructions or local prescribing information and may be accompanied by harmful physical and/or psychological effects.
- **Abuse:** Is defined as persistent or sporadic, intentional excessive use of a medicinal product, which is accompanied by harmful physical or psychological effects.
- **Medication error:** Is any unintentional error in the prescribing, dispensing, or administration of a medicinal product by a healthcare professional, subject, or consumer, respectively. The administration or consumption of the unassigned treatment and administration of an expired product are always reportable as medication errors. Cases of subjects missing doses of investigational product are not considered reportable as medication errors.
- **Product complaint:** Is defined as any written, electronic, or oral communication that alleges deficiencies related to the identity, quality, durability, reliability, safety, effectiveness, or performance of a drug or device after it is released for distribution. A special situation report form will only be completed if a complaint is associated with an adverse drug reaction.

All special situation events as described above must be reported to the Sponsor/designee within 24 hours of knowledge of the event. All AEs associated with these special situation reports should be reported as AEs or SAEs as well as recorded on the AE eCRF and/or the SAE report form. Details of the symptoms and signs, clinical management, and outcome should be provided, when available.

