This document is confidential.

1. Glossary of Abbreviations

Abbreviation	Description
AE	Adverse Event
ATC	Anatomical Therapeutic Chemical
BMI	Body Mass index
bpm	beats per minute
C	Celsius
CBC	complete blood count
CFU	colony-forming units
CI	Confidence Interval
CTCAE	Common Terminology Criteria for Adverse Events
DSMB	Data and Safety Monitoring Board
ECG	Electrocardiogram
eCRF	Electronic Case Report Form
FEF ₂₅₋₇₅	Forced Expiratory Flow between 25 and 75% of the FVC
FEV ₁	Forced Expiratory Volume in 1 second
FVC	Forced Vital Capacity
GLI	Global Lung Function Initiative
ICH	International Conference on Harmonization
kg	kilogram
L	liter
LCQ	Leicester Cough Questionnaire
MedDRA	Medical Dictionary for Regulatory Activities
mmHg	millimeters of mercury
Pa, P. aeruginosa	Pseudomonas aeruginosa
PFU	plaque-forming unit
PT	Preferred term
QOL-B	Quality of Life Bronchiectasis Questionnaire
QTc	corrected QT interval
QTcB	corrected QT interval using Bazett's formula
QTcF	corrected QT interval using Fridericia's formula

This document is confidential.

Abbreviation	Description
RR	respiratory rate
SAP	Statistical Analysis Plan
SD	Standard Deviation
SGRQ	Saint George's Respiratory Questionnaire
SOC	System Organ Class
SOP	Standard Operating Procedure
TEAE	Treatment Emergent Adverse Event
WHO	World Health Organization

This document is confidential.

2. Purpose

The purpose of this statistical analysis plan (SAP) is to ensure that the data listings, summary tables and figures which will be produced, and the statistical methodologies which will be used, are complete and appropriate to allow valid conclusions regarding the study objectives.

This SAP is created based on Protocol Number AP-PA02-201 version 5.0, dated 19 December 2023. This SAP will outline the planned analyses by Syneos Health (SYNH) to support the completion of the Clinical Study Report (CSR). This SAP describes in detail the statistical methodology and the statistical analyses to be conducted for the above-mentioned protocol. The planned analyses identified in this SAP follow the Statistical Principles for Clinical Trials such as International Council for Harmonisation (ICH) guidelines, E4 and E9.

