5.3. Exploratory Efficacy Endpoints

The exploratory endpoints include the following:

- Anti-Pseudomonas antibiotic sensitivity of *P. aeruginosa* isolates at specified time points during the study;
- Change in *P. aeruginosa* density from Baseline;
- Change from Baseline of in vitro sensitivity of subject *P. aeruginosa* isolates to AP-PA02 and/or individual phage components;
- Change in spirometry from Baseline;
- Change from Baseline levels of induced sputum neutrophil elastase; and
- Change in quality of life as assessed by the following questionnaires:
 - Quality of Life-Bronchiectasis Questionnaire;
 - Leicester Cough Questionnaire; and
 - Saint George's Respiratory Questionnaire.

This document is confidential.

6. Analysis Sets

Subjects who enrolled prior to the first DSMB meeting and received AP-PA02 were given a lower dose (3×10^{11} PFU/day) of AP-PA02. After the first DSMB meeting, a decision was made to increase the dosage of AP-PA02 to 6×10^{11} PFU/day (see [Section 8.5](#)). Unless noted otherwise, summary outputs by treatment groups will exclude subjects who were enrolled on the study prior to the first DSMB meeting that occurred on 01Nov2023 and received AP-PA02.

Subjects who were enrolled on the study prior to the first DSMB meeting but received placebo will be 'pooled' with the subjects who were enrolled after the first DSMB meeting as the 'pooled' placebo group within their respective cohorts.

All subjects will be included in the listings.

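### The Protocol as supplied and the SAP state different AP-PA02 doses, and the SAP separates dose levels by date relative to the first DSMB meeting rather than by dose received

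*SAP*

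**What the plan says.** **Dose in the Protocol.** Section 5.5.3 states that "The AP-PA02 dose will be administered to each subject as 2 fractionated doses per treatment day". It then lists 1.5×10^11 PFU per administration, 3×10^11 PFU per day and 3×10^12 PFU per 10-day course. The synopsis repeats these figures. No other dose level appears in the supplied text. Section 3.1.1 allows dose levels to be modified after DSMB review and caps the daily dose at 4×10^12 PFU.

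**Dose in the SAP.** Section 8.5 attaches the same three figures to the period before the first DSMB meeting and adds: "After the first DSMB meeting, the dose was doubled". Section 6 says: "After the first DSMB meeting, a decision was made to increase the dosage of AP-PA02 to" 6×10^11 PFU/day. The SAP states that it is based on Protocol "version 5.0, dated 19 December 2023". Section 13, on changes from the Protocol, records none.

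**Who is in the AP-PA02 arm.** Under SAP 6, unless noted otherwise, summaries by treatment group "exclude subjects who were enrolled on the study prior to the first DSMB meeting that occurred on 01Nov2023 and received AP-PA02". Placebo subjects from both periods are pooled within cohort. SAP 7.6 allows some key summaries to be repeated with the removed subjects added back, but describes them as "subjects who received AP-PA02 and were dosed prior to the first DSMB meeting".

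**The concern.** There are two linked problems.

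First, someone reading the dosing section of the supplied Protocol and someone reading the SAP come away with different daily doses for subjects treated after the meeting. The clause permitting modification explains how a change could happen. It does not state the dose that resulted.

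Second, the retained AP-PA02 arm is meant to represent the doubled dose, but membership depends on a calendar date. SAP 6 says that AP-PA02 subjects enrolled before the meeting had the lower dose. It makes no matching statement that every later enrolee had the higher one. By the SAP's own account the decision to increase came after the meeting, so the cut-off precedes the change by an unstated interval. Any AP-PA02 subject enrolled in that interval and given the lower dose would stay in the arm.

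What is at stake is the dose to which the primary comparison and the safety tables are attributed.

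**Working it through.** **1. The documents' dose figures.**
- Daily: 2 × 1.5×10^11 = 3×10^11 PFU, as in Protocol 5.5.3 and SAP 8.5.
- Course: 10 × 3×10^11 = 3×10^12 PFU, as stated.
- Doubled: 2 × 3×10^11 = 6×10^11 PFU/day, as in SAP 6. The implied course total is 6×10^12 PFU.
- Share of the ceiling: 6×10^11 / 4×10^12 = 15%.

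The SAP's figures agree with one another, and the doubled dose lies inside the Protocol's limit. What differs is the dose stated for the later period.

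**2. The rule applied to each type of AP-PA02 subject.**

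| Enrolled | Dose received | Place under SAP 6 | Consistent with dose? |
|---|---|---|---|
| Before the meeting | Lower (as SAP 6 states) | Excluded from summaries | Yes |
| After the meeting | Doubled | Retained | Yes |
| After the meeting | Lower | Retained | No |

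Only the third row is a problem. Nothing in the SAP rules it out: there is no date of first dispensing at the higher dose and no statement of what later enrolees received.

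**3. Whether another planned output would reveal the third row.**
- SAP 6.1 groups safety subjects by treatment received, and SAP 9 groups efficacy subjects by randomized treatment. Neither mentions dose level.
- Exposure (SAP 8.5) is summarised as days, minutes and number of doses.
- Compliance (SAP 8.6) is administrations given over administrations expected, 20 for a full course. A lower-dose subject with 20 administrations scores 100%.
- No exposure or compliance summary uses PFU.
- The SAP 7.6 repeat is optional and uses *dosed* where SAP 6 uses *enrolled*.

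**4. Weight of one such subject.** Protocol 9.2.4 plans 24 per cohort at 2:1, so 24 × 2/3 = 16 active per cohort. That total includes the subjects SAP 6 excludes, and the retained number is not given. As an assumption, take the first meeting at 10% or 50% enrolment (the review points in Protocol 3.1.1), even cohorts, exact 2:1 allocation and no replacement:

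| First meeting | Enrolled of 48 | Active, both cohorts | Active per cohort excluded | Active per cohort retained | One subject |
|---|---|---|---|---|---|
| None excluded (reference) | – | – | 0 | 16 | 1/16 = 6.25% |
| 10% | 4.8 | 3.2 | 1.6 | 14.4 | 1/14.4 = 6.9% |
| 50% | 24 | 16 | 8 | 8 | 1/8 = 12.5% |

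With one lower-dose subject, the arm's mean daily dose would be (15×6 + 3)/16 = 5.81×10^11 PFU in a 16-subject arm, or (7×6 + 3)/8 = 5.63×10^11 PFU in an 8-subject arm, instead of 6×10^11.

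**The case against.** Several stronger readings are tempting, and the documents do not support them.

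- **That the doubling breaches the Protocol or creates overdoses.** Protocol 8.6 defines overdose by a quantity "which is above the maximum recommended dose according to the Protocol". The explicit daily maximum in the Protocol is 4×10^12 PFU, and 6×10^11 is 15% of it. Modification after DSMB review is allowed. The gap is in documentation.
- **That subjects randomized up to 7 days before first dose could straddle the meeting and be misclassified.** SAP 6 says AP-PA02 subjects enrolled before the meeting were given the lower dose. Taken at its word, that closes this route.
- **That the 48 days from the meeting to the cited Protocol version measure a rollout lag.** No text links the start of the higher dose to that version.
- **That later subjects were in fact under-dosed.** No such subject is documented. Preparation and dispensing text is largely redacted and handling details sit in a Pharmacy Manual, so how the change reached sites cannot be judged.
- **That the supplied Protocol is the version the SAP cites.** The title page is not available, so part of the mismatch could come from comparing different versions.

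The other side can also say that the study has no formal power calculation, that the primary analysis reports confidence intervals without p-values, and that all subjects appear in listings. These points limit the consequences. They do not repair the rule: the third row of the table in the working stays open, and no summary that uses PFU would show it.

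**Conclusion.** The point holds in a limited form. The dose statements in the supplied Protocol and the SAP differ two-fold for the period after the first DSMB meeting, and SAP 13 does not acknowledge it. Separately, SAP 6 and 7.6 use two different date-based criteria to separate dose levels, and neither uses dose received.

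Misclassification is possible in one direction only: a lower-dose subject enrolled after the meeting and kept in the doubled-dose arm. It is not shown to have happened. Each such subject would be about 6% of a full 16-subject arm. Under the assumptions in the working, the figure is about 7% to 12.5% of the retained arm. The defect in the SAP rule does not depend on which Protocol version was supplied; the mismatch between the documents may.

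**What to change.** 1. Reconcile the dose statements in the Protocol synopsis and 5.5.3 with SAP 6 and 8.5. This review takes no view on which dose is right.
2. In SAP 6 and 7.6, define the excluded and retained AP-PA02 groups by the dose level actually received, with one criterion in both places.
3. Before the study team is unblinded, have the unblinded statistician confirm from dispensing and administration records that a dose level can be assigned to each AP-PA02 subject. Protocol 5.5.5 requires an inventory of drug received and dispensed but does not say that PFU level per subject is recorded, so this needs checking.
4. List any subject whose dose differs from what the date rule would assign.
5. Record the change in SAP 13.

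The cost is wording in two documents and one data check by unblinded personnel. No new data collection is needed if the records already carry dose level.
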